### **NRI incorporating Multiple Imputation (NRI-MI)**

The Non-Responder Imputation incorporating Multiple Imputation (NRI-MI) will be carried out for all the missing TSH values in the steps similar to the ones described above for NRI-C, with the exception of Step 1.2.

**Step 1.2. Imputing Responder Status:** In the imputed datasets from Step 1.1, the responder status (yes/no) will be derived from the TSH values at the end of Titration Period and the end of Stabilization Period according to the normal reference range (0.45-4.12 mIU/L, inclusive) based on the imputed values with the following exception: For participants who prematurely discontinue from the study due to lack of efficacy, adverse events related to study drug, or death, the non-responder status will be assigned to these participants in the imputed datasets regardless of the imputed values.

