6.7. Intervention after the End of the Study

Intervention after the EOS is not applicable.

7. Discontinuation of Study Intervention and Participant Discontinuation/Withdrawal

A premature discontinuation will occur if a participant who signs the ICF and receives intervention ceases participation in the study, regardless of circumstances, before the completion of the protocol-defined study procedures.

Reasons for discontinuation from the study intervention and/or the study may include the following commonly used or other acceptable terms (definitions are provided in [Appendix 5](#)):

- Adverse event
- Death
- Lost to follow-up
- Non-compliance with study drug
- Other
- Physician decision
- Pregnancy
- Site terminated by Sponsor
- Study terminated by Sponsor
- Withdrawal by participant

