7.1. Discontinuation of Study Intervention

If a clinically significant finding is identified after enrollment, the Investigator or qualified designee will determine if the participant can continue treatment with the study intervention and if any change in the participant's management is needed. Any new clinically relevant finding should be reported as an AE. All efforts should be made to follow the participant until the EOS to minimize the occurrence of missing data.

If a pregnancy is reported, see [Appendix 7](#) and Section 8.3.5 (Pregnancy) for procedures.

See the [Schedule of Activities](#) for data to be collected at the time of study intervention discontinuation and follow-up and for any further evaluations that need to be completed.

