10.5. Appendix 5: Standard Discontinuation Criteria

[figure not shown]
CDISC Submission Value	CDISC Definition
Adverse event	Any untoward medical occurrence in a patient or clinical investigation subject administered a pharmaceutical product and which does not necessarily have a causal relationship with this treatment. An adverse event (AE) can therefore be any unintended sign (including an abnormal laboratory finding), symptom, or disease temporally associated with the use of a medicinal (investigational) product, whether or not related to the medicinal (investigational) product. For further information, see the ICH Guideline for Clinical Safety Data Management: Definitions and Standards for Expedited Reporting (modified from ICH E2A) Synonyms: side effect, adverse experience. See also serious adverse event, serious adverse experience. (CDISC glossary)
Completed	To possess every necessary or normal part or component or step; having come or been brought to a conclusion (NCI)
Death	The absence of life or state of being dead (NCI)
Lack of efficacy	The lack of expected or desired effect related to a therapy (NCI)
Lost to follow-up	The loss or lack of continuation of a subject to follow-up
Non-compliance with study drug	An indication that a subject has not agreed with or followed the instructions related to the study medication (NCI)
Other	Different than the one(s) previously specified or mentioned (NCI)
Physician decision	A position, opinion or judgment reached after consideration by a physician with reference to subject (NCI)
Pregnancy	Pregnancy is the state or condition of having a developing embryo or fetus in the body (uterus), after union of an ovum and spermatozoon, during the period from conception to birth. (NCI)
Protocol deviation	An event or decision that stands in contrast to the guidelines set out by the protocol (NCI)
Screen failure	The potential subject who does not meet one or more criteria required for participation in a trial
Site terminated by Sponsor	An indication that a clinical study was stopped at a particular site by its Sponsor (NCI)
Study terminated by Sponsor	An indication that a clinical study was stopped by its Sponsor (NCI)
Technical problems	A problem with some technical aspect of a clinical study, usually related to an instrument (NCI)
Withdrawal by subject	An indication that a study participant has removed itself from the study (NCI)

CONFIDENTIAL

Protocol No. 3014-201-002

Armour Thyroid

[figure not shown]

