### **10.1**

### **PRIMARY EFFICACY ENDPOINT AND ANALYSES**

The primary efficacy endpoint is the achievement of TSH values within the normal reference range of 0.45 to 4.12 mIU/L, inclusive, at both the end of the Titration Period and the end of the Stabilization Period (sustained TSH responder). The primary estimand is the difference in the percentage of sustained TSH responders between the Armour Thyroid and synthetic T4 study intervention groups in the ITT Population. The number and percentage of sustained TSH responders will be summarized by treatment group in the ITT Population. Participants with a missing TSH value at either the end of the Titration Period or at the end of the Stabilization Period will be handled based on Non-Responder Imputation incorporating multiple imputation to handle missing data due to Covid-19 (NRI-C), as outlined later in this section.

The non-inferiority (NI) hypothesis test for the primary efficacy endpoint, based on the ITT Population, will be performed at a 1-sided 2.5% level of significance (equivalent to a two-sided 5% level of significance). The null hypothesis is that Armour Thyroid is inferior to synthetic T4, which will be tested against the alternative hypothesis that Armour Thyroid is non-inferior to synthetic T4, as follows:

$$H_0: p_A - p_T \leq -\Delta \text{ versus } H_a: p_A - p_T > -\Delta$$

Where:  $p_A$  and  $p_T$  are the proportions of TSH responders in the Armour Thyroid and synthetic T4 study intervention groups, respectively; [REDACTED]

The analysis of the primary efficacy endpoint will be performed on the ITT Population using stratum-adjusted Mantel-Haenszel by age group (age < 65 years or  $\geq$  65 years) as described in ([Agresti 2013, p. 231](#)).

The stratified proportion difference is

$$\hat{d}_{MH} = \left( \sum_h \hat{d}_h w_h \right) / \left( \sum_h w_h \right)$$

where  $\hat{d}_h$  is the proportion difference in stratum h and  $w_h = n_{h1} \cdot n_{h2} / n_h$ .

The proportion difference in stratum h is computed as

$$\hat{d}_h = \hat{p}_{h1} - \hat{p}_{h2} = (n_{h11} / n_{h1.}) - (n_{h21} / n_{h2.})$$

where  $\hat{p}_{h1}$  is the proportion of TSH responder for ATH and  $\hat{p}_{h2}$  is the proportion of TSH responder for synthetic T4 at stratum h.

The variance of  $\hat{d}_{MH}$  as

$$\hat{\sigma}^2(\hat{d}_{MH}) = \left( \hat{d}_{MH} \sum_h P_h + \sum_h Q_h \right) / \left( \sum_h w_h \right)^2$$

where

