#### **NRI incorporating Multiple Imputation (NRI-MI)**

The **Non-Responder Imputation** incorporating **Multiple Imputation** (NRI-MI) will be carried out for all the missing TSH values in the steps similar to the ones described above for NRI-C, with the exception of Step 1.2.

**Step 1.2. Imputing Responder Status:** In the imputed datasets from Step 1.1, the responder status (yes/no) will be derived from the TSH values at the end of Titration Period according to the normal reference range (0.45-4.12 mIU/L, inclusive).

For participants who prematurely discontinues from the study drug during the Titration Period due to lack of efficacy, adverse events related to study drug, or death, the non-responder status will be assigned to these participants in the imputed datasets regardless of the imputed values.

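### The NRI-MI sensitivity analysis uses leaving the study as its failure trigger for the primary endpoint but stopping study drug for the secondary, so one participant can be scored in a way the endpoint definitions rule out

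*SAP*

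**What the plan says.** SAP 10.1 and 10.2 each include a sensitivity analysis called NRI-MI. Missing TSH is multiply imputed under MAR, except that certain participants are set to non-responder in every imputed dataset. Step 1.2 defines who they are.

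- Primary endpoint (SAP 10.1): "For participants who prematurely discontinue from the study due to lack of efficacy, adverse events related to study drug, or death, the non-responder status will".
- Secondary endpoint (SAP 10.2), where death is again the third reason: "For participants who prematurely discontinues from the study drug during the Titration Period due to lack of efficacy, adverse events related to study drug".

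The three reasons are the same. The event differs: leaving the study in the first, stopping study drug during Titration in the second.

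Three other places bear on this:

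- SAP Appendix B defines the intercurrent event as premature discontinuation of study drug for both estimands, and says data after the event are used.
- The protocol has separate sections for stopping the intervention (7.1) and leaving the study (7.2). Section 7.1 says: "All efforts should be made to follow the participant until the EOS to minimize the occurrence of missing data". Section 9.4.1.4 says data after treatment discontinuation are collected and analysed where possible.
- The primary endpoint requires in-range TSH "at both the end of the Titration Period and the end of the Stabilization Period (sustained TSH responder"). The secondary endpoint requires only the first of these. Every sustained responder is therefore a titration responder.

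**The concern.** Being off drug but still in the study is a state the protocol plans for. The primary NRI-MI rule, read literally, does not reach it; the secondary rule does if the stop is in Titration. Two things follow.

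First, the two analyses can give one participant incompatible scores.

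Second, the primary NRI-MI treats a treatment-related drug stopper who stays in the study, in either period, exactly as plain MI does. The imputation model (SAP 10.1, Step 1.1) holds treatment group, age group, baseline TSH and, for the later value, end-of-Titration TSH. It has no term for being off drug. NRI-MI is the intermediate analysis between plain NRI, which fails every missing value, and plain MI, which fails none. For these participants it loses the feature that sets it apart from MI.

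At stake is the coherence of one pre-specified sensitivity analysis with its companion and with the estimand table.

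**Working it through.** The plan gives no figure on this point, so there is none to reproduce. The check is to apply both Step 1.2 rules as worded to the same participant.

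In the first four rows the participant stops drug for one of the three reasons and remains in the study; in the last, the participant leaves.

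| Pattern | Primary NRI-MI (10.1) | Secondary NRI-MI (10.2) | Allowed by the definitions? |
|---|---|---|---|
| Stop in Titration; end-of-Titration TSH missing, imputed in range; end-of-Stabilization TSH in range (observed or imputed) | Responder in that dataset | Non-responder | No |
| Same, but end-of-Titration TSH imputed out of range | Non-responder | Non-responder | Yes |
| Stop in Titration; end-of-Titration TSH observed in range; end-of-Stabilization TSH in range (observed or imputed) | Responder | Responder if the exception covers only missing values; non-responder if it covers every such stopper | Only on the first reading |
| Stop in Stabilization; end-of-Titration TSH in range; end-of-Stabilization TSH missing, imputed in range | Responder in that dataset | Responder | Yes, but the treatment-related stop is not counted as failure |
| Leaves the study in Titration | Non-responder | Non-responder | Yes |

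Across all combinations of stop period, leaving or staying, and TSH in or out of range at each time, there is one impossible combination: drug stopped in Titration, participant stays, both TSH values in range. Rows 1 and 3 are its missing and observed forms.

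With study-drug discontinuation as the common trigger, applied only where the endpoint TSH is missing:

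- Row 1 becomes non-responder on both endpoints.
- Row 3 becomes titration responder. It is sustained responder if the later value is observed in range, and sustained non-responder if it is missing.
- Row 4 becomes titration responder and sustained non-responder.

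No impossible combination is left, provided both endpoints are derived from the same imputed TSH values.

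**Size per participant.** Inputs: about 284 randomised 1:1, so about 142 per arm (SAP 4.1); non-inferiority margin 10 points (Protocol 9.4.1.2).

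- Crude rate: 1/142 = 0.70 points. At the protocol's 110 per arm it would be 1/110 = 0.91 points.
- Stratified difference with the SAP 10.1 weights, assuming equal arms within each age group: the weights sum to 284/4 = 71, and one participant contributes (1/2)/71 = 1/142. The result is the same.
- This is a ceiling. Averaged over the 100 datasets, the shift is the share of datasets in which the participant is scored a responder, divided by 142.

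The documents do not say how many participants would be affected. Assuming 1 to 3 in one arm and none in the other, the ceiling is 0.7 to 2.1 points.

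**The case against.** The strongest reply is that nothing decisive rests on this wording. NRI-C, the primary analysis, already scores a participant with a missing endpoint TSH as a non-responder unless the cause is solely COVID-19. The NRI sensitivity analysis does so without exception, and a tipping-point analysis is planned. NRI-MI relaxes those rules. This stands, and it limits the point to NRI-MI.

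The second reply is that the case is rare. Protocol Section 7 describes premature discontinuation as ceasing participation in the study, so in practice the two events may largely coincide. The schedule in SAP Table 4-1 has an Early Termination visit with TSH and no off-drug visit series. Entry to Stabilization is for participants in range at the end of Titration, so someone without that value is off the planned path to Visit 7. This stands as to frequency. It does not remove the contradiction, because the primary NRI-MI imputes both values if both are missing.

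Two stronger readings are tempting and are not supported.

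- A reader might infer a bias toward non-inferiority. The direction depends on which arm has more such stoppers, and the documents give no counts by arm. A multi-point shift would need an assumed imbalance with no source.
- A reader might infer that the lack-of-efficacy trigger cannot work because the reason list in Protocol Section 7 omits it. That list is open: "Reasons for discontinuation from the study intervention and/or the study may include the following commonly used or other acceptable terms". It refers to Appendix 5 for definitions, and Appendix 5 does define lack of efficacy: "The lack of expected or desired effect related to a therapy (NCI"). How sites would code such cases is not shown.

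**Conclusion.** The mismatch is real and minor. As worded, the two NRI-MI rules act on different events, and the primary rule departs from Appendix B. One pattern gives a sustained responder who is a titration non-responder. Drug stoppers who stay in the study, in either period, are handled in the primary NRI-MI as in plain MI. The contradiction itself arises only for stops during Titration.

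Each affected participant moves an arm's rate in this analysis by at most 0.7 points against a 10-point margin. That rests on about 142 participants per arm; the number affected is unknown and probably small. NRI-C, NRI, responder imputation, complete case and plain MI do not use this trigger and are unchanged.

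**What to change.** In Step 1.2 of NRI-MI in both SAP 10.1 and 10.2, make the trigger premature discontinuation of study drug for lack of efficacy, drug-related adverse event or death: at any time for the primary endpoint, during Titration for the secondary. State that it applies where the endpoint TSH is missing and that observed TSH after stopping drug is scored as observed, in line with Appendix B. Once the triggers match, no separate rule linking titration and sustained response is needed, and no protocol change is required.

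The cost is a wording change in the SAP, best made before unblinding. The primary NRI-MI result may come out slightly less favourable.

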### **Multiple Imputation**

The Multiple Imputation (MI) analysis will be carried out for all the missing TSH values regardless of reasons for missingness in the steps similar to the ones described above for NRI-C, with the exception of Step 1.2.

**Step 1.2. Imputing Responder Status:** In the imputed datasets from Step 1.1, the responder status (yes/no) will be derived from the TSH values at the end of Titration Period and the end of Stabilization Period according to the normal reference range based on the imputed values.

### **Tipping Point**

Tipping-point analysis will be performed to investigate the impact of missing TSH values on the study results, that is to identify difference of minimum numbers of Sustained TSH responders between treatment groups in the missing cohort which results in conclusion change ([Yan, Lee and Li, 2007](#)).

### **Stratified Newcombe Confidence Interval**

For the sensitivity analyses of Non-Responder Imputation, Responder Imputation, and Complete Case, the 2-sided 95% confidence interval for stratified proportion difference will also be performed in the ITT Population using stratified Newcombe confidence interval, which is based on a stratified method with Cochran-Mantel-Haenszel weights ([Yan and Su 2012](#)).

## 10.2

## SECONDARY EFFICACY ENDPOINTS

### **The Achievement of Titration TSH Response**

The achievement of titration TSH Response is defined as TSH values that are within the normal reference range of 0.45 to 4.12 mIU/L, inclusive, at the end of the Titration Period (Titration TSH Responder). The secondary estimand is the difference in the percentage of Titration TSH Responders between the Armour Thyroid and synthetic T4 study intervention groups in the ITT population. The number and percentage of titration TSH responders will be summarized by treatment group in the ITT Population along with the 2-sided 95% CI for the stratified proportion difference. The non-inferiority (NI) hypothesis test for the secondary efficacy endpoint, based on the ITT Population, will be performed at a 1-sided 2.5% level of significance (equivalent to a two-sided 5% level of significance). The analysis of the secondary efficacy endpoint will be performed on the ITT Population using stratum-adjusted Mantel-Haenszel by age group (age < 65 years or  $\geq$  65 years) as described in the Section 10.1 (Agresti 2013, p. 231).

The **Non-Responder Imputation** incorporating multiple imputation to handle missing data due to Covid-19 (NRI-C) will be performed for participants who have missing TSH values at the end of the Titration Period similar to the primary efficacy analysis outlined in Section 10.1.

### ***Sensitivity Analyses for the Secondary Efficacy Endpoint***

Participants who are missing TSH values at the end of the Titration Period will be assessed by the following sensitivity analyses. Additional sensitivity analyses will be performed if useful and appropriate.

#### **Non-Responder Imputation**

The non-responder imputation sensitivity analysis will be performed to investigate the impact of missing TSH values. If a participant has missing TSH value at the end of the Titration Period, then this participant will be imputed as a titration TSH non-responder.

#### **Responder Imputation**

The responder imputation sensitivity analysis will be performed to investigate the impact of missing TSH values. If a participant has missing TSH value at the end of the Titration Period, then this participant will be imputed as a titration TSH responder.

#### **Complete Case**

Participants who have not completed the Titration Period or who have missing TSH values at the end of the Titration Period will be excluded from the analysis.

#### **NRI incorporating Multiple Imputation (NRI-MI)**

The **Non-Responder Imputation** incorporating **Multiple Imputation** (NRI-MI) will be carried out for all the missing TSH values in the steps similar to the ones described above for NRI-C, with the exception of Step 1.2.

**Step 1.2. Imputing Responder Status:** In the imputed datasets from Step 1.1, the responder status (yes/no) will be derived from the TSH values at the end of Titration Period according to the normal reference range (0.45-4.12 mIU/L, inclusive).

For participants who prematurely discontinues from the study drug during the Titration Period due to lack of efficacy, adverse events related to study drug, or death, the non-responder status will be assigned to these participants in the imputed datasets regardless of the imputed values.

### **Multiple Imputation**

The Multiple Imputation (MI) analysis will be carried out for all the missing TSH values regardless of reasons for missingness in the steps similar to the ones described above for NRI-C, with the exception of Step 1.2.

**Step 1.2. Imputing Responder Status:** In the imputed datasets from Step 1.1, the responder status (yes/no) will be derived from the TSH values at the end of Titration Period according to the normal reference range.

### **Tipping Point**

[figure not shown]
Tipping-point analysis will be performed to investigate the impact of missing TSH values on the study results, that is to identify difference of minimum numbers of titration TSH responders between treatment groups in missing cohort which results in conclusion change (Yan, Lee and Li, 2007).

## **10.3 MULTIPLE COMPARISONS PROCEDURE**

The overall type I error rate will be controlled at a two-sided 0.05 level for the primary and secondary efficacy endpoints using the fixed sequential procedure in the following order:

- Step 1: Testing for non-inferiority of proportions of sustained TSH responders in the ITT Population.
- Step 2: Testing for non-inferiority of proportions of titration TSH responders in the ITT Population.

## **10.4 ADDITIONAL AND EXPLORATORY EFFICACY ENDPOINTS**

## **11.0 SAFETY ANALYSES**

The safety analysis will be performed on the Safety and Safety-T3 Populations. The safety parameters will include AEs, clinical laboratory measurements including fasting T3 and T4 (total T3, total T4, free T3 and free T4), vital sign values, ECG parameters, and physical examination findings. For each safety parameter of the clinical laboratory, vital sign, and ECG parameters, the last non-missing safety assessment prior to or on the first dose of study intervention will be used as the baseline for all analyses of that safety parameter. Continuous variables will be summarized by number of patients and mean, SD, median, minimum, and maximum values. Categorical variables will be summarized by number and percentage of patients.

### **11.1 ADVERSE EVENTS**

AEs will be coded using the Medical Dictionary for Regulatory Activities (MedDRA), Version 19.0 or newer.

An AE will be considered a TEAE if:

- The AE began on or after the date of the first dose of study intervention; or
- The AE was present before the date of the first dose of study intervention, but increased in severity or became serious on or after the date of the first dose of study intervention

An AE that occurs more than 35 days after the last dose of study intervention will not be counted as a TEAE.

An AE will be considered a TESAE if it is a TEAE that additionally meets any SAE criteria.

The number and percentage of participants reporting TEAEs in each study intervention group will be tabulated by system organ class and preferred term and by system organ class, preferred term, and severity.

The number and percentage of participants reporting treatment related TEAEs in each study intervention group will be tabulated by system organ class and preferred term. If more than 1 AE is coded to the same preferred term for the same participant, the participant will be counted only once for that preferred term using the most severe and most related occurrence for the summarizations by severity and by relationship to study intervention.

Summary tables will be provided for participants with SAEs and participants with AEs leading to discontinuation if 5 or more participants reported such events. Listings of all AEs, SAEs, and AEs leading to discontinuation by participant will be presented.

